#### Video behavior coding

Video records of the toy play session will be scored for certain qualitative and quantitative behaviors, including, *but not limited to*:

- The Toy Quality Scale (TQS): Qualities of the toy itself (i.e., are there moving parts, does the toy make noise, how soft is the toy? Is it a branded toy with a licensed character on it?). This coding system is being developed in CFRS.
- Parts and features of toys used by the child.
- Duration of time child spends with each toy.
- When playing with parent, how often, in what way, and for how long does the child solicit the parent’s involvement? How often, in what way, and for how long does the parent solicit the child’s involvement?
- Level of Play Complexity (taken from Bornstein et al., 1996; Cote & Bornstein, 2009, Suizzo & Bornstein, 2006):
  - (0) *default* (no play);
  - (1) *unitary functional activity* (e.g., throw the ball);
  - (2) *inappropriate combinatorial activity* (e.g., put the ball into a teacup): Was the toy used as intended or features of toy fully exploited?
  - (3) *appropriate combinatorial activity* (e.g., put the cup on the saucer);
  - (4) *transitional play* (e.g., put the telephone to the ear without speaking);
  - (5) *self-directed pretense* (e.g., drink from a cup);
  - (6) *other-directed pretense* (e.g., pretend to feed the doll);
  - (7) *sequential pretense* (e.g., dial and speak into the telephone); and
  - (8) *substitution pretense* (e.g., pretend the block is a telephone receiver and speak into it).

Note that all of these procedures described above are solely for research purposes, not for medical or clinical evaluation or treatment. Radiation is not used in this study.

There are no follow-up visits associated with this study. The study has no relations to any other existing protocol.

#### **d. End of participation**

Because this is a social and behavioral research project, transfer of care to assure continuity, the provision of additional medical care, and sharing information with health care providers is not applicable. When the project is complete, parents may request a summary of the findings from the study. However, all findings from the study will be anonymized.

Experimenters will not provide individual-level survey information to participants. This will aid in guarding against any possible negative feelings that could arise from families knowing their results (e.g., feeling inadequate as a parent because he or she did not score highly on the Knowledge of Effective Parenting Scale) or inappropriate use of the data by the family (e.g., using the score on the Vineland Adaptive Behavior Scale as part of a school entrance exam). If parents request a video of their session, we will not distribute a copy to them until the study is over. Parents must provide a written request for the video. We will not distribute the videos to parents until the completion of the study to guard against their sharing it with friends, neighbors, on social media, etc. Other people who view the video through these outlets could potentially become participants in the study without our knowledge. If these people ever do become participants, already having watched a video like this could confound their results and behaviors, weakening the scientific integrity of the study.

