**b. Consent procedures**

Permission for participation of minors will be obtained from parents/legal guardians. Parents will have the opportunity to carefully review the written consent form and ask questions regarding the study prior to signing. After the consent form has been filled out and parental permission is obtained, the parent and child may begin participation in the study.

Permission from only one parent is being requested. The permission of one parent is sufficient for compliance with 45 CFR 46.404, as the proposed research poses risk no greater than that ordinarily encountered in daily life or during the performance of routine physical or psychological examinations or tests (i.e., minimal risk).

At the time of the play session, CFRS staff will also obtain assent from the children to ensure that they want to participate in the study as well. Parents will be present during the assent process and will sign the bottom of the assent form to certify that they witnessed their child's assent.

Children between the ages of 4-5 will provide verbal assent. Researchers will sign the form to certify that they received assent from the participant. Language for verbal assent will be as follows:

"We are doing this project because we want to know more about how kids play with toys. If you join in, you will play with some toys. My friend here is going to use a camera to make a video of you while you play with the toys. Nobody will see the video except people who work with us, and we will keep the video private by putting it in a locked room. Then, I will ask you some questions. You might like playing with these toys, but you might not like it. If you do not want to play with them, you do not have to. We will get to learn about what kids like and how they think if you will help us. You will also get to play with some toys. If you do not want to play anymore, you do not have to. Just tell me if you do not want to play anymore! If you decide you want to stop, you can leave—I will not be upset. Anything that you say to me will be safe. Do you have any questions? Would you like to do this?"

Children over the age of 6 will be read the same statement and will be asked to sign a written assent form to indicate their willingness to participate.

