## **20. Confidentiality**

### **a. For research data and investigator medical records**

Child participants will be assigned ID numbers at the outset of the study. The key linking the ID numbers with the participants' identity and videos taken of the children will be kept in a locked filing cabinet in a room that is locked when unoccupied.

Electronic data will be kept in password-protected computers and servers. Only study investigators will have access to the samples and data. Data collected on paper will be de-identified through the use of the ID number assigned to the participant at the outset of the study. Data collected on paper will be entered into electronic spreadsheets. All participant identifying data except for subject numbers will be removed from these spreadsheets.

In addition, parents will have the option of indicating on the consent form whether or not they will allow the use of short video clips of themselves and their child at professional presentations and conferences. Parents may contact us to change their preferences for the public use of these videos at any time, both during or after the study.

Subject confidentiality will be maintained to the greatest extent possible. Research results will be labeled using a unique code. Publications will not include subject names nor will they contain personal identifying information.

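### The scripted assent tells children that only the team will see the video, while the protocol lets clips be shown at meetings and lets parents have a copy; the timing of clip use is also unstated

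*Combined protocol and SAP*

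**What the plan says.** Section 14b (Consent procedures) prints the words to be spoken to children aged 4 to 5 when verbal assent is sought. They include "Nobody will see the video except people who work with us". The same section adds "Children over the age of 6 will be read the same statement", after which those older children sign a written form.

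Two other sections allow viewing outside the team:

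- Section 20a (Confidentiality, research data) uses the consent form to ask parents "whether or not they will allow the use of short video clips of themselves and their child at professional presentations and conferences". It goes on: "Parents may contact us to change their preferences for the public use of these videos at any time, both during or after the study".
- Section 4d (End of participation) provides for a copy of the session video if the parent asks in writing, with the limit that "we will not distribute a copy to them until the study is over".

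Section 4d also explains the delay: "We will not distribute the videos to parents until the completion of the study to guard against their sharing it with friends". The scientific worry is that people who see a copy might later enrol, and "already having watched a video like this could confound their results and behaviors, weakening the scientific integrity of the study".

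**The concern.** The main issue is participant protection. A child is asked to agree to being filmed on the strength of an assurance that has no exceptions, and the same protocol provides for two exceptions. A parent's permission can authorise the use, but it does not make what the child was told accurate. Section 19 makes outside access to study data depend on the adult's consent and does not mention the child's assent. Section 5a accepts that a child's first name may be heard on the recording. Changing the script later would not alter what children who have already assented were told.

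The second issue is smaller and concerns the design. Section 4d treats earlier viewing of a session as a threat to the results and closes one route by holding back parents' copies. Section 20a opens another route, clips shown to outside audiences, and says nothing about when that may begin.

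**Working it through.** The plan states no figure on this point. The check is a comparison of the text, with two simple counts for scale.

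**Assent wording against permitted uses**

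| Who may see the recording | Script (14b) | Elsewhere in the protocol |
|---|---|---|
| Research team | Yes | Yes |
| Audience at a professional meeting | Ruled out | Allowed as short clips with parental opt-in (20a) |
| The child's parent, as a copy | Ruled out | Allowed on written request, after the study (4d) |

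The first row agrees and the other two conflict. Section 14b gives the script as the language to be used, so this is not a loose summary of an assent form kept elsewhere.

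**How many children hear the script**

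Inputs: 60 children in each of six age bands, 360 in all (accrual table); assent script from age 4 (14b). Ages are assumed to be spread evenly within bands.

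- 36-71 months: ages 48-71 months make up 24 of the 36 months, so 60 × 24/36 = 40.
- 72-107 months: 60.
- 108-144 months: 60.
- Total: 40 + 60 + 60 = 160, and 160/360 = 44%.

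Section 14b names ages 4-5 and then children over 6. If that is taken literally and six-year-olds are left out, the second of these bands gives 60 × 24/36 = 40. The total is then 40 + 40 + 60 = 140, and 140/360 = 39%.

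These are counts of children who hear the statement. It is untrue only for those whose parent opts in and whose clip is shown, or whose parent obtains a copy. With neither rate given, the range is 0 to about 160.

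**Timing of release**

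- Parents' copies: held until the study is over (4d).
- Clips: no start date or embargo (20a).
- Enrolment period: 360 dyads (3a) at an anticipated 5 children per week (4b) gives 360/5 = 72 weeks. This is the longest period in which a showing could precede a later child's session at that rate. No showing is scheduled in the documents.
- End of the hold: section 5a keeps the protocol open for as long as the data might have further research use, so the end of the study in 4d has no clear date.

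**The case against.** The strongest objections concern the timing point. Section 4d is directed at uncontrolled spread of session videos among friends, neighbours and social-media contacts, who are plausible recruits. Section 20a covers short clips, with opt-in, before professional audiences. Section 4b lists NIH websites, a listserv and social media as places to recruit, but not conference audiences, and no overlap is shown. A rule for one channel and silence on another is a gap, not a direct contradiction. This stands, and it is why timing is the minor part.

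A reader might infer from the phrase about during or after the study in 20a that clips will be shown while enrolment is open. The sentence does not say that. It governs when parents may change their preference. It is compatible with showings during the study, but the firm statement is only that no embargo appears.

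On the assent wording, it can be said that consent and assent pages are not among the documents available, so the written assent form or the consent form may disclose the clips or set a date. That cannot be excluded. It does not repair the spoken script, which is printed in full and read to both age groups. It can also be said that the parent is present at assent and takes part in the session, so treating the parent's own later copy as a breach is rather literal. That is fair, and the clips are the weightier of the two exceptions. Even so, section 4d itself foresees that parents might pass a copy on.

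**Conclusion.** The assent point holds on the printed text. The scripted assurance is absolute and does not fit sections 20a and 4d. It is untrue for any assenting child whose parent opts in and whose clip is shown, or whose parent obtains a copy. The number is between 0 and about 160 of 360, given even ages within bands and unknown opt-in and request rates. It would be wrong to read 160, or 44%, as the number misinformed; it is an upper bound.

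The timing point holds only as a minor one: a safeguard that the protocol justifies on scientific grounds is not extended to clips. A reader might infer that play scores are at material risk, or that there are 72 weeks of exposure. The documents support neither. Any bias is probably small, and 72 weeks is only the planned length of enrolment.

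The point is worth correcting because the remedy is cheap and the main fault lies in what children are told. It rests on the protocol text alone, without sight of the consent and assent forms.

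**What to change.** 1. **Section 14b.** Replace the sentence about who sees the video with one that matches the permitted uses, in language suited to the child. For example: *The people who work with us will watch the video. Your parent may get a copy later, and we may show short parts of it at meetings if your parent says that is okay.* Bring the rest of that sentence, on keeping the video private, and the written assent form for older children into line.

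2. **Sections 4d and 20a.** Apply one defined end point to every release of video outside the team, such as completion of the last play session. After that event no later participant can be influenced, so the reason given in 4d is met. Use the same event in both sections. Adding it to 20a alone would leave two different rules, because the present wording of 4d has no clear date.

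The cost is a few sentences in an amendment. The one practical loss is that no clips could be used at meetings during enrolment, about 72 weeks at the anticipated rate.

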## **5. Management of Data and Samples**

### **a. Storage**

Data will be stored according to NICHD and NIH policy. We will not collect any specimens or samples. All data will be stored permanently in an archival database by the National Institutes of Health. They will be retained for analysis in perpetuity. The Principal Investigator will maintain subjects' records after completion of the study.

In addition, data may be stored in a password-protected database via CTDB. For statistical analyses, data will be de-identified according to the Privacy Act, and when possible, by all 18 HIPAA identifiers. If a limited dataset is needed (for example to include dates), a user agreement will be executed. Only investigators or designees authorized to use CTDB will have access to the data.

The anonymity and rights of the study's participants and their families will be fully protected. The full proper names of participants will not appear on the video record or questionnaires, although it is possible that a child's first name might be used during the video recorded play session. All data will be tallied and analyzed without reference to individual names.

Child participants will be assigned ID numbers at the outset of the study, and the key linking the ID numbers with the participants' identity, as well as digital video records of the children filmed during the testing session, will be kept in a locked filing cabinet in a locked room when no researchers are present at the CFRS laboratory. ID numbers are linked with personal identifying information, and only the clinical site investigators or designees have access to it. The linkage is critical to interpretation of the data, as data will be compared across subject groups. No one other than members of the research team will have access to this linkage data without the explicit consent of the volunteer adult.

This protocol will be kept open as long as there is a possibility of future research use of the data. When there is no longer a need, data will be archived by the investigator in compliance with the requirements for retention of research records, or after IRB approval, destroyed or transferred to another repository.

Any loss or unanticipated destruction of data that would affect the scientific integrity of the study will be reported to the IRB as an unanticipated problem.

**b. Data (*if applicable*: including genomic data) and sample sharing plan**

At this time, we do not have any approved collaborators, but anticipate this in the future. Other investigators (both intramural and extramural to the NIH) may wish to study these data. Before sharing the data approved outside collaborators, we will submit an amendment with specific information about the other investigators/institutions and what data/samples will be shared. IRB approval will be sought prior to any sharing of data.

The broad public sharing of data generated by this project is not possible until participant consents to share data publicly are obtained. Data generated by this study will be made available through vetted collaborations and IRB approvals in the interim. This study will be registered on our NICHD Intramural website (<https://science.nichd.nih.gov/confluence/display/cfr/Home>) along with the above justification.

Any use of this data by a secondary party after submission to a designated repository must be shared by that party according to the permissions granted by the original consent form of the study participants unless additional permissions are obtained. Secondary parties must adhere to the NIH Human Data Sharing guidelines for broad data sharing and to the limitations for use set forth by the Institutional Certification associated with this project. Access to identified data for secondary research will only be granted after IRB review or OHSRP clearance, as applicable.

Any publications and presentations authored or co-authored using data generated by this project will clearly indicate where the data will be available and how to access it. The repository(s) and funding source will also be acknowledged in any publications and presentations.

## **6. Additional Considerations**

**a. Research with investigational drugs or devices**

This provision is not applicable to our research. We will not be using investigational drugs or devices.

**b. Gene therapy**

This provision is not applicable to our research. We will not be using gene therapy.

## **7. Risks and Discomforts**

Participation in this study involves minimal risk. The probability and magnitude of harm or discomfort anticipated with the research are not greater in and of themselves than those ordinarily encountered in daily life. We will minimize risk by choosing stimulus toys that are approved as safe by the CPSC. It is possible that while completing the questionnaires, participants may find that some questions touch on areas of personal sensitivity and may experience discomfort when answering the questionnaires. Parents and children may decline to answer any question.

All procedures are non-invasive. Previous work conducted in the CFRS reassures us that, while some parents may initially feel slightly self-conscious while being observed (perhaps more so when being filmed), in a short period of time they relax and enjoy being involved in a study that focuses on their child and his or her development. Parents will be assured that if their child becomes distressed by any procedure, the session will be interrupted and she will be allowed to soothe the child and resume any caregiving responsibilities.

## **8. Subject Safety Monitoring**

We will monitor the play room and end the play session if a child engages in a potentially dangerous action. Because this is social and behavioral research, we will not use toxicity tables, etc. for subject safety monitoring. Participating in this study is voluntary, and participants may withdraw at any time without penalty. At the time of the play session, we will ask each child if s/he would like to play with toys. If a child says that they do not want to play, or decides in the middle of the study that they want to play no longer, the child will be allowed to withdraw without penalty. Parents may also elect to stop their own or their child's participation in the study at any time.

## **9. Outcome Measures**

### **a. Primary outcome measures**

The primary study outcomes are the video-coded measures of age-appropriateness and play complexity. We will examine differences in the mean scores of play among toys from the three age groups that are chronologically adjacent (i.e., the differences in outcomes for a given age group with the age-appropriate toy in comparison with toys from the same toy category just below and just above that age group).

### **b. Secondary outcome measures**

Our other secondary outcome measures include the following:

- Parts and features of toys used by the child
- Duration of time child spends with each toy
- Child preference for the toys based on child-report (smiley face Likert scale)
- Number of times and duration of time the child solicits the parent's or friend's involvement during play

## **10. Statistical Analysis**

### **a. Analysis of data/ study outcomes**

For our primary outcome measure, our independent variables will be the age group for which the toy is aimed (younger vs. age-appropriate vs. older; within-subject) and the age group of the child (6 groups; between-subject), and our dependent variables will be the video-coded measures of play. The statistical methodology that we will use to analyze this question is a repeated-measures ANCOVA with up to five covariates. Our five covariates include the following: (1) toy characteristics, (2) child temperament, (3) family socioeconomic status, (4) child preferences for the toy, and (5) parenting knowledge.

For our secondary outcome of interest (how children play alone vs. with parent), we will conduct another repeated-measures ANCOVA with condition (alone vs. with parent) and designated toy age (younger vs. age-appropriate vs. older) as within-subject factors and child age (6 groups) as a between-subject factor. Again, our dependent variables will be the video-coded measures of play. We will also use the same five covariates mentioned above: (1) toy characteristics, (2) child temperament, (3) family socioeconomic status, (4) child preferences for the toys, and (5) parenting knowledge.

Both of the repeated-measures ANCOVA designs will also be employed when we examine the dependent variables of secondary interest noted in section 9b, such as parts and features of toys used by the child, duration of time child spends with each toy, child preference for the toys based on child-report (smiley face Likert scale), and the number of times and duration of time the child solicits the parent's involvement during play. The independent variables mentioned above would remain the same.

We do not have any planned interim analysis. Our criteria for significance is alpha = .05. Due to the protocol's design, unplanned missingness will be low. Missing data procedures, such as Full Information Maximum Likelihood and Multiple Imputation, will be used.

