## **2. Study Objectives**

### **a. Primary objectives**

The primary objective of the current observational study is to categorize traditional and contemporary children's products and toys into age appropriate groups based on their intended use. To do this, we will examine differences in child play among toys from the three chronologically adjacent age groups to determine the differences in play for a given age group with an age-appropriate toy in comparison with toys from the same toy category intended for the next youngest and the next oldest age groups.

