#### **c. Study procedures**

##### **Procedure**

Participants will be 720 parents and their children from 6 months to 12 years of age. We will recruit children divided into the following six age groups:

- 6-11 mos

- 12-18 mos (1-1.5 years)
- 19-35 mos (1.5-2 years)
- 36-71 mos (3-5 years)
- 72-107 mos (6-8 years)
- 108-144 mos (9-12 years)

Each child will first :

- Play alone
- then*
- Play with parent

Each child in each age group will receive children's products and toys from 6 of the 9 following categories:

- (1) Construction toys (e.g., blocks, interlocking building materials)
- (2) Exploratory toys (e.g., clay, sand toys)
- (3) Games & Puzzles
- (4) Instructional toys (e.g., books, science kits)
- (5) Sports, Recreational, & Outdoor Equipment
- (6) Imaginative play toys (e.g., puppets, dolls, dress up materials)
- (7) Small Wheeled Vehicles (e.g., car toys)
- (8) Arts & Crafts toys
- (9) Musical toys (e.g., musical instruments)

- Prior to testing, all toys used in this project will be inspected for safety hazards by staff trained in conducting safety evaluations of toys for the Consumer Product Safety Commission. Toys will be inspected for small parts, mechanical hazards (cord length, magnet strength, etc.), lead, and phthalates. All small parts will be removed from toys for children under age 3, and toys will be replaced with similar ones if any mechanical hazards, lead, or phthalates are identified.
- There is a large body of research regarding children's gravitation towards and play with sex-stereotyped toys (O'Brien & Huston, 1985; Caldera et al., 1989). Although child gender is an important factor to consider when studying the qualities of toys, the current study will use gender neutral toys as stimuli in an attempt to eliminate any potential gender confound.

The experimenters will select three representative target toys from each toy category. Target ages are determined by the manufacturer's suggested age.

- Children will be presented with one of three (counterbalanced) toys targeted for their age group from 6 of the 9 toy categories.
- When presented, each target toy will be paired with two additional toys from the same toy category: one targeted to the age group just below and one from the age group just above the target toy.

- Children will receive novel sets of toys when switching from playing alone to play with parent.

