### **b. Power analysis**

For our primary research question, a power analysis revealed that 360 parent child dyads split across 6 age groups and 3 within-subject designated toy ages (younger vs. age-appropriate vs. older) is sufficient to detect a medium effect ( $f = .25$ ) for between-subjects and within-subjects effects and their interactions in a RM-ANCOVA with 5 covariates (power = .80 and alpha = .05).

For our secondary research question, a power analysis revealed that 360 parent child dyads split across 6 between-subject age groups, 2 within-subject conditions (alone vs. with parent), and 3 within-subject designated toy ages (younger vs. age-appropriate vs. older) is sufficient to detect a medium effect ( $f = .25$ ) for within- and between-subject effects and their interactions in a RM-ANCOVA with 5 covariates (power = .80 and alpha = .05).

For both our primary and secondary research questions, our five covariates include the following: (1) toy characteristics, (2) child temperament, (3) family socioeconomic status, (4) child preferences for the toys, and (5) parenting knowledge. Subject dropouts will be replaced with other comparable subjects who complete the protocol.

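### Toy characteristics are a listed covariate in both repeated-measures ANCOVAs; entered per toy they can absorb part of the toy-age difference under study, and the plan does not say how they enter

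*Combined protocol and SAP*

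**What the plan says.** Section 10a specifies the primary analysis as "a repeated-measures ANCOVA with up to five covariates". Its factors are designated toy age (three levels, within child) and child age group (six levels, between children). The covariate list opens with "1) toy characteristics, (2) child temperament, (3) family socioeconomic status" and ends with child preference for the toy and parenting knowledge. For the alone-versus-with-parent model the same section says "We will also use the same five covariates mentioned above". Section 10b claims power "for between-subjects and within-subjects effects and their interactions in a RM-ANCOVA with 5 covariates" and repeats, for both research questions, that "our five covariates include the following: (1) toy characteristics" and the other four.

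The target of the primary analysis is set elsewhere. Section 2a compares play with an age-appropriate toy against "toys from the same toy category intended for the next youngest and the next oldest age groups". Section 9a puts it as "the differences in outcomes for a given age group with the age-appropriate toy in comparison with toys from the same toy category", one step below and one step above. Section 4c fixes how a toy gets its age: "Target ages are determined by the manufacturer's suggested age".

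Section 2b, objective 2, asks how toy qualities vary with that same manufacturer's age. Section 4c describes a Toy Quality Scale scored on the toy itself (moving parts, noise, softness, branding), and a questionnaire on toys and their features. No section defines toy characteristics as a covariate, names the measure, or says whether it takes one value per toy or one per child.

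**The concern.** The three toys in a set differ in manufacturer's age, and toys for different ages plausibly differ in their features. The Introduction reviews studies in which movable parts, responsiveness and realistic detail change how children play. If features are part of the reason that a child plays differently with an older toy, they are part of the effect to be measured. Adjusting for them changes the question to what the age label adds once features are held equal, which is not the comparison in sections 2a and 9a.

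The Introduction's rationale for statistical control (the ecological model of play) names sociodemographic, play-partner and child characteristics. It does not name toy characteristics, and no other reason for adjusting for them is given.

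The results feed the revised Age Determination Guidelines. A small feature-adjusted toy-age difference could be read as saying that toys for adjacent ages are played with alike, when their features are what makes them differ.

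Child preference for the toy raises a related problem. It is also specific to the toy, it is a secondary outcome in section 9b, and section 10a applies both ANCOVA designs to it. No exception is stated for the analysis in which it is the outcome.

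**Working it through.** **1. The plan's own figure.** Inputs from section 10b: N = 360, 6 child age groups, 3 toy ages, f = 0.25, 5 covariates, alpha 0.05, power 0.80. The within-child correlation and the power formula are not stated.
- A conservative form for the toy-age by child-age interaction uses noncentrality f² × N = 0.0625 × 360 = 22.5, with (6 − 1)(3 − 1) = 10 and (360 − 6 − 5) × 2 = 698 degrees of freedom.
- Power is 0.9255, and 0.80 needs N = 265. The other primary-model forms tried give more.
- The three-way interaction of the secondary model has (6 − 1)(2 − 1)(3 − 1) = 10 numerator degrees of freedom, and power is 0.92.

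The claim that 360 is sufficient therefore holds, although exactly 0.80 is not recovered. With three covariates instead of five the denominator becomes (360 − 6 − 3) × 2 = 702 and power is still 0.9255. Nothing in the power statement depends on this covariate.

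**2. Per-toy entry, one common slope.** Code toy age a = −1, 0, +1. Let features rise by g per step, let play rise by b per unit of feature, and let d be the step in play not carried by features. For any toy-age contrast,

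adjusted contrast = unadjusted contrast − b × (same contrast in mean features).

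- *Older minus younger.* The unadjusted value is 2(d + bg), the feature contrast is 2g, and the adjusted value is 2d. With share s = bg/(d + bg), the fraction left is 1 − s.
- *Own-age minus the mean of its two neighbours.* The feature contrast is 0 − (−g + g)/2 = 0, so nothing is removed when features rise evenly across bands.
- *Toy age by child age.* The shift is b times the difference between bands in their feature contrasts. It is zero only if features step equally in every band, which the documents do not say.

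**3. Simulation check.** Layout from the documents: 360 children in 6 bands of 60, 6 of 9 categories, 3 counterbalanced toys per category, toys one band either side. Assumed: true step 0.50 per toy-age level (older minus younger 1.00), child and residual SD 0.7, and the share carried by features.

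| Share carried by features | 0 | 25% | 50% | 75% | 100% |
|---|---|---|---|---|---|
| Older minus younger, no covariate | 1.00 | 1.00 | 1.00 | 1.00 | 1.00 |
| Covariate per toy | 1.00 | 0.75 | 0.50 | 0.25 | 0.00 |
| Covariate as child average | 1.00 | 1.00 | 1.00 | 1.00 | 1.00 |

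The second row is 1 − s, so it confirms the algebra and does not estimate a size.

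Two other shapes of effect, with per-toy entry, give for own-age minus the mean of its neighbours:
- play peaking at the own-age toy: 0.498 without the covariate, 0.498 with it;
- play driven wholly by how well features fit the child's age: 0.024 without, 0.025 with.

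**4. One average per child.** A value that is constant within a child cancels from every within-child difference if it enters as a main effect only, so the overall toy-age contrast is unchanged. The average does follow child age band, because toys are chosen around the band. It therefore competes with the between-band effects that section 10b also claims to power.

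**The case against.** Four points on the other side have weight.

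- *Per-toy entry is only one reading.* Classical repeated-measures ANCOVA takes one covariate value per subject, and on that reading the overall toy-age contrast is safe. This stands. But the Toy Quality Scale is scored on the toy, which makes per-toy entry an equally natural reading, and two analysts following section 10a could estimate different quantities.
- *The phrase up to five lets the primary model omit the covariate.* True, but no rule says when, so the choice could follow the results. The secondary model says the same five.
- *With three target toys per category, adjusting for nuisance features such as branding is reasonable.* True, and a sensitivity model keeps that information.
- *For the secondary outcomes, section 10a carries forward the independent variables and is silent on covariates.* So it does not positively state that preference will be adjusted for itself. It does carry forward both ANCOVA designs and states no exception.

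A reader might also infer that per-toy adjustment removes everything the features contribute. The documents do not support that. The primary comparison sets the own-age toy against both neighbours, and the Introduction ties toy needs to the child's age and stage. Effects of that shape can survive a common-slope covariate, as the check shows.

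**Conclusion.** The concern holds in a limited form. Toy characteristics are listed as a covariate in both models, they are plausibly part of the toy-age difference being measured, and their measure and level of entry are unspecified. Under per-toy entry with one common slope, the loss is the part of the toy-age difference that is linear in the features and equal across child ages, chiefly the older-versus-younger trend. If features carry none of the effect, there is no bias.

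The size is unknown. The documents give neither the relation of features to toy age nor the share of the effect that features carry, so the 1.00 to 0.00 range in the table restates an assumed input. No claim is made about precision.

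A reader might infer that a child-level average would erase the differences between child age bands. That would need child age to have no direct effect on play, and the Introduction says that play becomes more complex with age. What can be said is that the average overlaps with band and may distort those effects by an unknown amount.

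**What to change.** In sections 10a and 10b:

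1. Make the model without toy characteristics primary for the toy-age contrast and its interaction with child age, in both ANCOVAs.
2. Report the model with toy characteristics as a labelled sensitivity analysis. State the measure (for example the Toy Quality Scale) and whether it enters per toy or per child.
3. Do not use child preference as a covariate when it is the outcome. In the other models, treat it likewise as a sensitivity covariate.
4. Update the covariate count in both sections. Moving both items to sensitivity models leaves three covariates in the main models.

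The cost is wording plus one more labelled analysis, with no new data and no change to the 360 dyads. The downside is that the main model no longer adjusts for nuisance features such as branding; the sensitivity model shows whether that matters.
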